7.5 Efficacy

7.5.1 Overall Efficacy Summary

Efficacy analyses will be performed using the randomized subjects data set. For the non-inferiority endpoints, the analysis will also be performed in the evaluable subject data set. All analyses included in the hierarchical testing below, including the primary analysis, will use the randomized

subject data set. The analyses using the evaluable subject data set will not be included in the hierarchical testing.

All the main analyses will be conducted using values prior to rescue/intensification of treatment or treatment discontinuation. Values collected after this time will be excluded from analyses. Sensitivity analysis using data regardless of rescue or treatment discontinuation will also be performed for the primary efficacy endpoint to assess the robustness of the primary efficacy results.

The primary endpoint is the change in HbA1 from baseline at Week 24 visit. The primary endpoint will be tested for non-inferiority for saxagliptin plus dapagliflozin versus insulin at the $\alpha = 0.025$ level (one sided), within a non-inferiority margin of 0.30%. If non-inferiority is demonstrated for the primary endpoint, the statistical tests for the secondary efficacy endpoints will be performed. The secondary endpoints then will be tested sequentially in the order that they appear below and in the objectives section of the protocol. Each comparison will be tested at the $\alpha = 0.05$ (two-sided) level. Statistical tests between the dapagliflozin plus saxagliptin group and insulin group will be only performed for a given secondary endpoint if all previous sequential tests are statistically significant. Otherwise, the testing procedure will stop at the secondary endpoint that does not reach statistical significance. These secondary endpoints are all testing superiority, with the exception of the fourth and fifth bullets below which are testing non-inferiority.

- Change from baseline in total body weight at Week 24 (tested for superiority)
- Proportion of subjects with confirmed hypoglycemia [defined as: blood glucose ≤ 70 mg/dL (3.9 mmol/L) recorded in the hypoglycemia module of the CRF] at Week 24 (testing superiority)
- Proportion of subjects achieving a therapeutic glycemic response, defined as HbA1c $< 7.0\%$, without any reported hypoglycemia (for the duration of the Short-term Period) at Week 24 (testing superiority)
- In a sub-study, change from baseline in the mean value of 24-hour glucose readings measured by Continuous Glucose Monitoring (CGM) at Week 2 (testing non-inferiority, using a non-inferiority margin of 12 mg/dL)
- Proportion of subjects achieving a therapeutic glycemic response, defined as HbA1c $< 7.0\%$ at Week 24 (testing non-inferiority, using a non-inferiority margin of 10%)

Analyses of secondary and exploratory endpoints specifically designed for sub-studies (CGM) will be performed using the subsets of the Randomized Subjects data set for the sub-studies.

7.5.2 Primary Efficacy Analysis

The primary endpoint is the change in HbA1 from baseline at Week 24 visit. The primary endpoint will be tested for non-inferiority for saxagliptin plus dapagliflozin versus insulin at the $\alpha = 0.025$ level (one sided). The primary analysis of the change in HbA1c from baseline at Week 24 visit will be based on a longitudinal repeated measures analysis using 'direct likelihood'. The model will use subjects in the primary efficacy data set (i.e., randomized subjects data set) who have a baseline assessment and at least one post-baseline open-label

treatment period assessment. The SAS procedure PROC MIXED will be used. The preferred model will include the fixed categorical effects of treatment, week, randomization stratification factor (background medication of metformin alone vs. metformin + SU) and treatment-by-week interaction as well as the continuous fixed covariates of baseline measurement and baseline measurement-by-week interaction (see Model 7.1.2.1 in Section 7.1.2). An unstructured matrix for the within-subject error variance-covariance will be used. The denominator degrees of freedom will be calculated according to the Kenward-Roger method. A number of back-up models are defined in the Core statistical analysis plan (Section 7.1.2) in case of non-convergence of the preferred model or other issues. Data collected outside the analysis window (defined in Section 8 of this SAP) after subjects discontinued study medication will also be excluded from the primary analysis. Point estimates and 95% confidence intervals for the mean change within each treatment group as well as the difference in mean change between the saxagliptin plus dapagliflozin versus insulin will be calculated. If the upper limit of the 95% confidence interval of the difference is $< 0.3\%$, then saxagliptin plus dapagliflozin as add-on therapy to metformin with or without SU will be considered non-inferior to insulin as add-on therapy to metformin with or without SU.

Sensitivity Analyses

The following sensitivity analyses will be carried out for the primary end point:

- Primary analysis will be repeated using Evaluable Subjects data set.
- Primary analysis will be repeated using all available values regardless of rescue or treatment discontinuation
- An ANCOVA analysis using values prior to rescue or treatment discontinuation (LOCF will be used if the week 24 value is not available)
- Analyses to address missing values (described below in section 7.5.3)
 - Analysis using multiple imputation return-to-baseline
 - Tipping point analysis

7.5.3 Handling of missing efficacy data

Missing data in this study may result from patients discontinuing from the study prematurely or missing intermediate visits or selected assessments while remaining on study. Every reasonable effort will be made to obtain the protocol-required data for all study assessments that are scheduled for all patients who have been enrolled. For efficacy analyses, missing observations will not be imputed, except those inherited from the mixed model repeated measures (MMRM) which assumes that data are missing at random (MAR).

MAR refers to missingness that is independent of missing responses, conditionally on observed responses and covariates. As the imputation strategy should always consider the dropout patterns and the time-course of the efficacy measurements by treatment, the pre- and post-withdrawal values will be assessed to understand the impact of dropouts on the efficacy results.

The primary efficacy endpoint of HbA1c data will be visually examined to explore the missingness patterns by (1) plotting each individual patient's HbA1c change trajectory in completers, side-by-side with those from the early study drug withdrawal, and by (2) plotting the early study drug withdrawal's last HbA1c change data, overlaid with the box plot by visit from completer population. Two additional methods of sensitivity analyses will be performed to compare the results from an MAR-based analysis versus an MNAR-based analysis under several MNAR scenarios. The first method is the return-to-baseline using Multiple Imputation in which patients with missing data known or believed to have discontinued protocol therapy were assumed to have a washout ("return to baseline") of any potential treatment effect. More specifically for each imputation of the multiple imputation, for those subject with missing Week 24 measurements for HbA1c. The second method is the Tipping Point Analysis, which assumes that patients from the experimental treatment arm who discontinue treatment or initiate a rescue therapy would have values worse by some amount "delta" compared to efficacy values of similar patients who continue with study treatment and do not require rescue. The detailed analysis plan and implementation of these methods are described in section 7.5.3.1, and 7.5.3.2.

The analysis for the treatment difference will be based on an ANCOVA model with change from baseline to week 24 as the dependent variable and covariate/factors of treatment group, randomization strata, and baseline HbA1c.

7.5.3.1 MMRM Model for Change from Baseline Based on Return-to-Baseline Multiple Imputation

The return-to-baseline MI (Multiple Imputation) imputes the change from baseline to Week 24, and samples will be drawn from a Normal distribution with mean 0 and variance of pooled data. Let $X = (X_{\text{obs}}, X_{\text{miss}})$ be the complete data at Week 24. X is consisted of observed measurements X_{obs} and the missing observations X_{miss} . In return-to-baseline imputation, when X is change from baseline (CHG), each missing observation X_{miss} is imputed by a random draw from a Normal distribution with mean 0 and variance v_{imp} :

$$X_{\text{mis}} \sim N(0, v_{\text{imp}}),$$

The variance v_{imp} is calculated from the observed changes:

$$v_{\text{imp}} = (1 + 1/N_c) v_c,$$

where v_c is the variance of the change among completers across all treatment arms, and N_c is the number of completers.

An ANCOVA model will be used to analyze the imputed datasets for change from baseline with treatment group and randomization strata as fixed factors and Baseline HbA1c as a covariate. The least square mean (LS mean) estimates will be combined using Rubin's combination rules for statistical inference. All available measurements will be used including observations post-rescue and post-discontinuation of treatment.

In this study, the primary analysis is comparing Saxagliptin + Dapagliflozin + Metformin group to control group Insulin Glargine + Metformin. The above approach will be conducted using the Insulin Glargine + Metformin as the control group.

7.5.3.2 Tipping Point Analysis based on ANCOVA Model for Change from Baseline Using Multiple Imputation

In order to address the impact of missing data due to initiation of rescue therapy, or premature treatment discontinuation on the primary efficacy analysis, a Tipping Point Analysis using multiple imputation will be performed to compare the results from analysis assuming a missing at random (MAR) mechanism versus analysis assuming a missing not at random (MNAR) mechanism. The specific MNAR assumption that will be considered in this framework is that patients from the experimental treatment arm who discontinue study treatment prematurely or who initiate a rescue therapy would have, on average, their efficacy values post rescue/post treatment discontinuation worse by some amount delta compared to efficacy values of similar patients who continue with the study treatment and do not require rescue therapy. Delta is considered a sensitivity parameter representing a degree of departure from the MAR assumption. The aim of the Tipping Point Analysis is to find a “tipping point” corresponding to a value of delta where the study conclusion of a non-inferior treatment effect would no longer hold. An interpretation of clinical plausibility of the assumption underlying the tipping point will be provided.

The tipping point approach based on multiple imputation of values at time points after treatment discontinuation or initiation of rescue can be performed with a specified adjustment (referred to as delta adjustment or shift) applied to values imputed under an MAR-based imputation model for the appropriate subset of patients. In order to find a tipping point, a series of imputations will be performed with increasing values of delta.

For the primary endpoint which is a continuous variable, we will use an additive delta adjustment (a shift) as follows:

$$Y_{j(adj)}^{(m)} = Y_{j(imp)}^{(m)} + \delta$$

Where -

- $Y_{j(imp)}^{(m)}$ are values imputed using a MAR-based imputation model in the m^{th} imputed dataset, $m=1, \dots, M$ (number of imputations)
- δ is a mean shift (delta adjustment) parameter for adjusting imputed values

The main steps in the implementation of the Tipping Point Analysis are described below.

Step 1: Investigate missing data patterns in the source data (containing observed values prior to initiation of rescue therapy or premature study treatment discontinuation). If missing data have both monotone and non-monotone patterns, use a multivariate regression imputation model and the Markov chain Monte Carlo (MCMC) method to partially impute non-monotone data under the MAR assumption. The variables used as explanatory variables for imputation include Randomization strata, HbA1c baseline, and post-baseline HbA1c at each time point. The imputations will be done separately within each treatment arm. If there are not enough observations to properly estimate covariance parameters, then stratification variables could be removed from the MCMC step, and/or the treatment arm can be included as an explanatory variable in the model.

As a result, each imputed dataset will only have a monotone missing data pattern.

Step 2: Impute remaining monotone missing data using an MAR-based regression imputation model for all patients who discontinued study treatment prematurely or initiated a rescue therapy. Apply a shift (an additive delta adjustment) to imputed values of patients in the experimental treatment arm (Saxagliptin + Dapagliflozin + Metformin). The variables used as explanatory variables for imputation include Treatment, Randomization strata, HbA1c baseline, and post-baseline HbA1c at each time point.

Imputations with delta adjustment described above will be performed with varying values of delta in order to perform a series of analyses with progressively larger values of delta until a tipping point is reached. A tipping point will correspond to the smallest value of delta for which the primary hypothesis (non-inferiority) is no longer held (the upper bound of 95% confidence interval of the difference is greater than 0.3).

Step 3: At each level of delta, analyze each of multiple imputed datasets using the same ANCOVA model as used for the primary analysis. Combine estimates obtained from multiple imputed datasets based on Rubin's combination rules.

Step 4: Using 95% upper CI, find the tipping point, ie, the value of delta parameter for which the primary non-inferiority hypothesis is no longer held. In this study, we will compare the non-inferiority of Saxagliptin + Dapagliflozin + Metformin vs. Insulin Glargine + Metformin for each Delta value. We will find the delta value at which the test of non-inferiority hypothesis is no longer held. A clinical interpretation about the plausibility of the assumptions underlying the tipping point will be provided.

7.5.4 Secondary Efficacy Analyses

If non-inferiority is demonstrated for the primary endpoint, the statistical tests for the secondary efficacy endpoints will be performed. The secondary endpoints then will be tested sequentially in the order that they appear in the objectives section of the protocol. Each comparison will be tested at the $\alpha = 0.05$ (two-sided) level for superiority. Statistical tests between the dapagliflozin

plus saxagliptin group and insulin group will be only performed for a given secondary endpoint if all previous sequential tests are statistically significant. Otherwise, the testing procedure will stop at the secondary endpoint that does not reach statistical significance.

The continuous secondary endpoints (i.e., the change from baseline in total body weight, the change from baseline at Week 24 visit in the mean value of 24-hour glucose readings obtained from CGM) will be analyzed using a longitudinal repeated measures analysis, similarly to the one used for primary efficacy analysis. The proportion of subjects achieving HbA1c < 7.0% will be analyzed using the methodology of Zhang, Tsiatis, and Davidian and Tsiatis, Davidian, Zhang, and Lu with adjustment for baseline HbA1c value and/or the stratification factor. The other binary endpoints (hypoglycemia endpoint and composite response endpoints of glycemic control with hypoglycemia) will be analyzed using logistic regression with adjustment for baseline HbA1c value and/or the stratification factor. In addition to point estimates and 95% confidence intervals, p-values will be calculated for all secondary endpoints. However, no claim will be based on endpoints for which the statistical testing is not performed for the endpoint as per the testing strategy as described above. A clear distinction will be made between p-values whereby claims can and cannot be made. All secondary efficacy analyses will use subjects in the primary efficacy data set (i.e., randomized subjects data set) who have a baseline assessment and any post-baseline open-label treatment period assessment.

For the two secondary endpoints which are tested for non-inferiority, the analysis will be repeated using evaluable subjects data set to examine the robustness of the results. The non-inferiority margins for the two secondary endpoints testing for non inferiority are specified in Table 7.5.4-1.

Table 7.5.4-1: Non-inferiority margins specified for primary/secondary endpoints

Secondary Endpoint	Non-inferiority Margin
Change from baseline in HbA1c at Week 24	0.30%
Change from baseline in mean 24-hour glucose readings measured by Continuous Glucose Monitoring (CGM) at Week 2	12 mg/dL
Proportion of subjects achieving a therapeutic glycemic response, defined as HbA1c < 7.0% at Week 24	10%

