3.2 Secondary Objectives

- To compare the mean change from baseline in total body weight with co-administered saxagliptin 5 mg and dapagliflozin 10 mg plus metformin with or without SU versus titrated insulin glargine plus metformin with or without SU after 24 weeks of open-label treatment.
- To compare the proportion of confirmed hypoglycemia [defined as: blood glucose \leq 70mg/dL (3.9 mmol/L) recorded in the hypoglycemia module of the CRF] with co-administered saxagliptin 5 mg and dapagliflozin 10 mg plus metformin with or without SU versus titrated insulin glargine plus metformin with or without SU during 24 weeks of open-label treatment.
- To compare the proportion of subjects achieving a therapeutic glycemetic response, defined as HbA1c < 7.0%, without any hypoglycemia, with co-administered saxagliptin 5 mg and dapagliflozin 10 mg plus metformin with or without SU versus titrated insulin glargine plus metformin with or without SU after 24 weeks of open-label treatment.
- To examine whether the change from baseline in the mean value of 24-hour glucose readings measured by Continuous Glucose Monitoring (CGM) with co-administered saxagliptin 5 mg and

dapagliflozin 10 mg plus metformin with or without SU is non-inferior to titrated insulin glargine plus metformin with or without SU after 2 weeks of open-label treatment.

- To examine whether the proportion of subjects achieving a therapeutic glycemic response, defined as HbA1c < 7.0%, with co-administered saxagliptin 5 mg and dapagliflozin 10 mg plus metformin with or without SU is non-inferior to titrated insulin glargine plus metformin with or without SU after 24 weeks of open-label treatment.

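### SAP Section 7.5.4 puts the ranked CGM mean-glucose secondary at Week 24 and under superiority, whereas the objectives, the hierarchy and its own margin table make it Week 2 non-inferiority

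*SAP*

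**What the plan says.** Section 7.5.4 names the continuous secondaries that receive the repeated-measures model. One of them is "the change from baseline at Week 24 visit in the mean value of 24-hour glucose readings obtained from CGM". The same section says that each secondary comparison is made at the 0.05 level, ending "two-sided) level for superiority", with no exception in that sentence. It adds that "p-values will be calculated for all secondary endpoints".

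Later in the section the text changes: "For the two secondary endpoints which are tested for non-inferiority, the analysis will be repeated using evaluable subjects data set". Table 7.5.4-1 then gives a 12 mg/dL margin for "Change from baseline in mean 24-hour glucose readings measured by Continuous Glucose Monitoring (CGM) at Week 2".

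Elsewhere the SAP is consistent:

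- Section 3.2, fourth objective: the combination "is non-inferior to titrated insulin glargine plus metformin with or without SU after 2 weeks of open-label treatment".
- Section 4.2, item 4: CGM mean glucose at Week 2.
- Section 7.5.1: "These secondary endpoints are all testing superiority, with the exception of the fourth and fifth bullets below which are testing non-inferiority". The fourth bullet is CGM mean glucose "measured by Continuous Glucose Monitoring (CGM) at Week 2 (testing non-inferiority, using a non-inferiority margin of 12 mg/dL".
- Section 4.3, item 2: mean CGM glucose at Weeks 12 and 24 is exploratory. Section 7.5.5 rules out statistical testing of any exploratory endpoint.

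**The concern.** Section 7.5.4 misstates the fourth ranked secondary twice. It names a visit that the SAP elsewhere treats as exploratory and untested, and its general sentence on hypotheses leaves no room for the two non-inferiority tests. That second error also covers the fifth secondary, HbA1c < 7.0% at Week 24 (margin 10%).

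The endpoint is part of the alpha-controlled sequence. Testing stops at the first secondary that fails, so the fourth step decides whether the fifth may be tested and claimed.

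The error would not show itself in programming. CGM is collected at Weeks 2, 12 and 24 (Section 2.1), and the repeated-measures model gives between-treatment estimates at all time points (Section 7.1.2). An analyst who followed Section 7.5.4 to the letter would obtain a plausible Week 24 superiority result. The study is also open-label, with sponsor personnel aware of allocation, although analyses by arm wait for the short-term database lock (Section 2.3). A gatekeeping test should have a single reading before that lock.

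**Working it through.** **1. The texts side by side**

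| Place in SAP | Visit | Hypothesis | Margin |
|---|---|---|---|
| 3.2, fourth objective | Week 2 | non-inferiority | not given |
| 4.2, item 4 | Week 2 | not given | not given |
| 7.5.1, fourth bullet | Week 2 | non-inferiority | 12 mg/dL |
| 7.5.4, general sentence on testing | not given | superiority, all secondaries | none |
| 7.5.4, list of continuous secondaries | **Week 24** | not given | none |
| 7.5.4, last paragraph | not given | non-inferiority for two secondaries | refers to table |
| Table 7.5.4-1 | Week 2 | implied by title and column heading | 12 mg/dL |
| 4.3, item 2 | Weeks 12 and 24 | exploratory, untested (7.5.5) | none |

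Four places give Week 2 for the secondary endpoint and only one gives Week 24, 22 weeks later (24 − 2). The only 12 mg/dL margin belongs to Week 2. Section 10, which lists changes from the protocol, records no change of CGM visit or hypothesis.

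**2. The SAP's own figures**

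The SAP states no power for the CGM endpoint. Its sample size rests on the primary endpoint (Section 5: margin 0.30%, SD 1.1%, one-sided 0.025, 90% power, true difference 0):

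- n per arm = 2 × (1.960 + 1.282)² × 1.1² / 0.30² ≈ 283, against 284 stated. Power at 284 is 90.1%.
- 284 / 0.95 ≈ 299 per arm, 598 in total, as stated.

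These figures reproduce, and none of them depends on the disputed text.

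**3. What the hypothesis wording changes**

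Let d be the observed difference in CGM change, saxagliptin plus dapagliflozin minus glargine, with lower values better and standard error SE.

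- Non-inferiority passes if d + 1.96 × SE < 12, that is d < 12 − 1.96 × SE.
- Superiority passes if d + 1.96 × SE < 0, that is d < −1.96 × SE.
- The thresholds differ by 12 mg/dL for any SE.
- At a true difference of 0, the chance of a superiority result in favour of the combination is Φ(−1.96) = 2.5%, for any SE.

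**4. Illustration with an assumed SD**

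The SAP gives no SD for the CGM change, so 25 to 50 mg/dL is an assumption. With about 125 per arm (Section 2.1), SE = SD × √(2/125), and non-inferiority power at a true difference of 0 is Φ(12/SE − 1.96):

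| Assumed SD (mg/dL) | SE | Pass as non-inferiority | Pass as superiority |
|---|---|---|---|
| 25 | 3.16 | 96.7% | 2.5% |
| 30 | 3.79 | 88.5% | 2.5% |
| 35 | 4.43 | 77.4% | 2.5% |
| 40 | 5.06 | 66.0% | 2.5% |
| 50 | 6.32 | 47.5% | 2.5% |

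**The case against.** The best reply is that no careful reader would be misled. Section 7.5.1 sets the ranked list, the hypothesis types and the margins, and expressly exempts the fourth and fifth secondaries from superiority. The end of Section 7.5.4 and its table do the same in substance. On ordinary reading, a specific exception with margins overrides a loose general sentence. The Week 24 phrase sits in a parenthesis that only says which endpoints receive the repeated-measures model, and for the testing order Section 7.5.4 defers to the objectives. The 12 mg/dL shift and the 2.5% arise only if all of this is ignored, and 2.5% is simply the one-sided error rate at a true difference of zero.

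Much of this stands. The intended reading can be recovered, the superiority point is a conflict within the section rather than a change of plan, and the figures describe the literal reading only. The power range rests on an assumed SD and does not carry the conclusion.

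The reply does not remove the contradiction. No text supports Week 24 as the ranked visit. Section 7.5.4 links the endpoint to its model, so a gatekeeping test should not have to be reconstructed from other sections.

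**Conclusion.** The concern holds: Section 7.5.4 is wrong as written on the visit, and contradicts both Section 7.5.1 and itself on the hypothesis. The wrong visit affects one of the five ranked secondaries; the unqualified superiority wording affects two, the fourth and fifth. Under the literal superiority reading, the passing threshold for the CGM difference moves by 12 mg/dL. This follows from the SAP's margin and a two-sided 95% interval and needs no assumed SD. The 2.5% chance of passing further assumes a true difference of zero, which the SAP uses in planning the primary endpoint but does not state for CGM. The correction should be made before the short-term database lock. It is not grave, because Week 2 non-inferiority with the 12 mg/dL margin is plainly intended.

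**What to change.** In Section 7.5.4:

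1. Give Week 2, not Week 24, as the visit for the CGM mean-glucose secondary.
2. Limit the superiority statement to the first three secondaries. State that the fourth and fifth are tested for non-inferiority, with the margins in Table 7.5.4-1.

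Mean CGM glucose at Week 24 stays exploratory and untested, as Sections 4.3 and 7.5.5 already provide. The cost is two wording corrections in one SAP section. They need no new data and leave the objective, endpoint, margin, model and sample size unchanged.
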